
The following participant withdrawal criteria may be implemented in determining when and how to withdraw participants from the trial/investigational product treatment.

Drug Discontinuation Criteria:

The subject's participation may be terminated for safety precautions based on any of the following by the study investigator. 1) Drug-related severe adverse event; 2) UTI requiring intravenous antibiotics; 3) Diagnosis of systemic absorption; 4) Diagnosis of nephrotoxicity; 5) Diagnosis of ototoxicity; 6) Diagnosis of renal failure

Temporary Discontinuation Criteria:

Situations of temporary discontinuation of study drug followed by subsequent resumption of study drug are: 1) Resolution of an adverse event, especially in cases where it is determined that the study drug was unlikely to have caused the event. 2) Resolution of a symptomatic UTI.

Withdrawal from Study:

A participant may withdraw from study participation at any time. Whatever data has been collected at the time of study termination will be evaluated by the PI for use in the final study database. If a participant is terminated from the study, the investigator will have the option to recruit an additional participant. Of withdraw from the study was due to an adverse event, participants will be followed until complete resolution of the adverse event that was possibly or definitely drug-related.

2. Statistical Plan: Data will first be summarized. We will use means with associated standard deviation, median with associated interquartile range and full range (min-max) to summarize continuous variables. Categorical variables will be summarized with frequency count and standard deviation. We will perform 2 types of analyses: pre-post differences within each group and between group comparisons of the differences. To evaluate the pre-post changes in each group, we will use paired t-test. To compare the changes between the 3 groups, we will use ANOVA test. If the ANOVA test yields significant results, we will perform follow-up 2 by 2 group comparisons using 2-sample t-tests. If the underlying assumptions of these tests are not satisfied, we will use the non-parametric equivalent tests instead.

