Urine collected for cultures will be collected as a clean-catch midstream technique from an immediately installed urine catheter or as a suprapubic aspiration from an installed catheter (52). For participants having a suprapubic catheter, the catheter will be clamped for 20 to 30 minutes until at least 5 mL of urine can be collected. The catheter will then be unclamped, and urine will be allowed to flow into a sterile plastic container. In those that use intermittent catheterization, participants will be required to first cleanse the urethral area with a castile soap towelette. A sterile 12 French straight catheter is inserted through the urethra into the bladder. The first portion of the urine stream should flow into the toilet in order to reduce the opportunities for contaminants to enter into the urine stream. The urine midstream is then collected into a clean container (any excess urine will be emptied into the toilet), Urine samples will be placed in

sterile storage vials and stored at 4C for less than 3 hours and sent to the Outpatient Care Center, Jewish Hospital for analysis. Symptomatic UTIs will be defined as a participant complaint of symptoms consistent with UTI (cloudy/foul smelling urine, fever, chills, increase in bladder and/or lower extremity spasms, worsening dysreflexia, leakage, or pain) combined with a positive leucocyte esterase and/or nitrates on dipstick urinalysis or a urine microscopy with > 10 WBC/HPF (white blood cells/high powered field) with a urine culture with >10⁵ bacteria/ml (46). Note that urine smell and cloudiness alone (i.e. without other symptoms) are not considered UTI signs, given their high prevalence in this catheterizing population. All cultured microorganisms will be identified to the species level and quantified as colony-forming units per ml (cfu/ml⁻¹) (16). If the microorganism(s) cultured is/are resistant to three or more different antimicrobial agents to which the microorganism would normally be susceptible, it will be defined as being multi-resistant. If a participant is diagnosed having a symptomatic UTI necessitating systemic antibiotics by the study physician/nurse practitioner, he/she will follow standard of care treatment under provider oversight. The study physician/nurse practitioner will recommend whether or not continuation of either the instillation or clamping protocol is appropriate for the participant during systemic antibiotic treatment.

5. Blood Draw

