University of Louisville Hospital and Frazier Rehab Institute evaluates approximately 300 chronic SCI outpatients each year. We also have a database of over 5,000 people with SCI who have expressed interest in participating in our research programs. We will select individuals to assure that there is a minimum of 25% women to adequately represent the percentage in the SCI population.

All SCI research participants, irrespective of gender, will be selected based on the following:

Inclusion Criteria

- At least 18 years of age;
- Non-progressive spinal cord injury;
- Stable medical condition;
- Bladder dysfunction as a result of spinal cord injury
- History of recurrent UTIs (defined as 3 or more within the past year or 2 or more within the past 6 months).

Exclusion Criteria

- Signs or symptoms of serious UTI that requires the use of systemic antibiotics;
- Use of any urine-acidifying agent, bladder irrigant, or systemic antibiotic within the previous 2 weeks;
- Participants colonized with gentamicin-resistant bacteria on baseline urine culture or a gentamicin allergy/sensitivity;
- Participants with known hearing loss and/or renal disease;
- Pregnant at the time of enrollment or planning to become pregnant during the time course of the study.

A. Screening and Enrollment

Potential research participants will be identified by our research database (UofL IRB 06.0647) and contacted by research staff prioritized by the initial date they entered the database and provided with general information regarding the research study. If the individual is interested in learning more about the study, the clinical coordinator will set up an info session via teleconference or a meeting at Frazier Rehab Institute. The designated project leader and clinical coordinator will attend the info session and the project leaders (Drs. [name] and [name]) will describe the project including the time commitment, the general design of the study, the interventions and the randomization process. Specific questions from the potential research participant will be answered.

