After the research participant signs the consent document, an Eligibility Checklist is completed by the research participant attesting to the eligibility requirements. This is placed in the research medical record along with supporting source documentation. These will be reviewed by the research manager and the principal investigator. The eligibility checklist will be signed by the person verifying eligibility and by the Principal Investigator who is responsible for final determination of eligibility. All source documentation for eligibility will be placed in the research medical report. We will request past medical records to determine eligibility. For research participants injured within a month of enrollment, an AIS examination would need to have been completed within four weeks of enrollment. For all other time points (three months, six months, one year, or 2 years post-injury) an AIS examination will need to be completed within three months of enrollment. If the individual has not had an AIS exam within the appropriate time point the research medical core staff will conduct the AIS exam. In consult with the medical core staff, the investigator will determine eligibility based on the medical history and the study inclusion/exclusion criteria and the research participants Attestation eligibility form. The regulatory research manager will do periodic internal audits of all enrolled research participants research medical report to ensure compliance of documentation.

C. Costs and Compensation

Participation in this study will require no additional study related costs to the research participant, unless they are injured. The participant or the participant's insurance company will be billed for all office visits, tests, medications, and procedures that are part of routine medical care outside of this research study. Participants will not be billed for the office visits, tests, medications, and procedures that are done for this research study. The charges for these items will be paid by the study. Participants will be responsible for paying co-pays associated with any office visit, test, medication, or procedure outside of this research study. Participants will be informed that some insurance companies will not pay for medical bills for individuals in research studies. It will be made clear that is the responsibility of the research participant to find out what costs, if any, the insurance company will cover before taking part in the study. The study

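### The within-arm pre-post UTI test sets a historical count against a protocol-defined on-study count, so it can be significant from a change in measurement alone

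*Combined protocol and SAP*

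**What the plan says.** The Statistical Plan (II.B.2) sets out "pre-post differences within each group and between group comparisons of the differences". For the first: "To evaluate the pre-post changes in each group, we will use paired t-test". For the second: "To compare the changes between the 3 groups, we will use ANOVA test". Two of the three power statements in that section concern the paired test with 12 participants and an SD of 1.7: 80% for a mean drop of 1.5 symptomatic UTIs, and 97% for a drop of 2 in 6 months.

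The pre-study UTI information that the protocol describes serves eligibility. The inclusion criterion (III, Human Subjects) reads "History of recurrent UTIs (defined as 3 or more within the past year or 2 or more within the past 6 months", with no urine-test requirement attached. Under III.B, "an Eligibility Checklist is completed by the research participant attesting to the eligibility requirements"; supporting source documents are filed with it, and "We will request past medical records to determine eligibility".

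The study's own definition is in item 4 of the research procedures, Urine Sample Collection and Culture: "Symptomatic UTIs will be defined as a participant complaint of symptoms consistent with UTI", "combined with a positive leucocyte esterase and/or nitrates on dipstick urinalysis or a urine microscopy with > 10 WBC/HPF", followed by a culture criterion of more than 10^5 bacteria/ml. Smell or cloudiness without another symptom does not count.

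Figure 2 gives the screening phase 5 days. III.A puts the treatment period at 80 days.

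**The concern.** A paired test assumes that both members of the pair are the same measurement. Here the later count consists of episodes that met a complaint-plus-urine-test rule. The earlier count is a history whose source, look-back period and definition the plan does not state. Past episodes that were diagnosed more loosely, or treated without the required tests, would enter the first count and would not have entered the second.

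The protocol's background section (I.D) makes this plausible. It describes a lack of consensus on diagnosis in this population, lists cloudy or malodorous urine among qualifying symptoms, and cites guidance that accepts 10^3 cfu/mL, a hundredth of the study's culture threshold.

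At stake is the reading of the within-arm result. With 12 per arm, a significant drop under gentamicin could be reported as efficacy although a drop of the same origin would be expected in the control arms. This is distinct from regression to the mean after selection on recent UTIs, and from the different lengths of the two observation periods. Both are separate matters.

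**Working it through.** **1. Reproducing the plan's figures.** Inputs from II.B.2: n = 12, SD 1.7, two-sided alpha 0.05. Power comes from the noncentral t distribution with 11 degrees of freedom, noncentrality = drop × √12 / 1.7, critical value 2.201.
- Drop 1.5: noncentrality 3.06, power 79.4% (stated 80%).
- Drop 2: noncentrality 4.08, power 95.9% (stated 97%).

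Both agree to within 2 points. The smallest observed mean drop that reaches significance is 2.201 × 1.7 / √12 = 1.08 UTIs.

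**2. Why the baseline must be historical.** A 6-month count cannot be observed in 5 days of screening, and no run-in is described. Anyone with a serious UTI needing systemic antibiotics, or with systemic antibiotics in the previous 2 weeks, is excluded. A count observed at screening would be near zero and could not fall by 1.5 or 2. This is an inference; the plan does not name the source.

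**3. Size of the shift, on assumed inputs.** The documents give neither the baseline rate nor the share of historical episodes that would meet the study definition. Let b be the historical count per 6 months and p that share. With no treatment effect the expected false drop is b(1 − p). Putting this into the formula of step 1 gives the chance of a significant drop in one arm (false drop in brackets):

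| b | p = 0.9 | p = 0.8 | p = 0.7 |
|---|---|---|---|
| 2 | 5.6% (0.2) | 11% (0.4) | 20% (0.6) |
| 3 | 8.1% (0.3) | 20% (0.6) | 39% (0.9) |
| 4 | 11% (0.4) | 32% (0.8) | 61% (1.2) |

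The right comparison is 2.5%, because only significant drops are counted. The lowest rate that the inclusion criterion admits is 3 per year, or b = 1.5; there the chances are about 5%, 8% and 13%.

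**4. Dropping the fixed SD.** An SD of 1.7 at every b is generous to the concern. If both counts are Poisson with equal windows, the variance of the change is b + bp; at b = 3, p = 0.7 that is 5.1, an SD of 2.26. Simulation of three arms of 12 with no treatment effect gives, for b = 2, 3 and 4:
- p = 1 (no shift): 2.3–2.5%.
- p = 0.8: 9.5%, 12.5% and 15%.
- p = 0.7: 17%, 24% and 30%.
- p = 0.7, with an 80-day on-study count scaled up to 6 months: about 16%, 20% and 24%.

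At p = 0.7 with equal windows, at least one of the three arms shows a significant drop in 43–67% of trials.

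**5. The between-arm test.** In the equal-window simulations the three-arm ANOVA on changes rejects in 4.7–5.4% of trials, whatever p is. The shift is common to all arms and cancels.

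**The case against.** The strongest reply is that the hypothesis on symptomatic UTIs (1.1) is stated against controls, and that the randomised comparison of changes is unbiased. That stands. A reader might infer that the trial's efficacy conclusion is biased; neither the documents nor the simulation supports that.

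Second, the protocol does not say that history is self-reported. Source documents support the checklist, the principal investigator makes the final eligibility decision, and the International SCI UTI data set (item 8 of the research procedures) standardises symptom, dipstick and culture information. The UTI definition is not expressly limited to on-study episodes. This is fair, and it rules out saying that the baseline rests on recall alone. But no sentence applies the definition or the data set to past episodes, and the records are requested for eligibility.

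Third, the direction is not certain. Forgotten episodes would lower the earlier count, and frequent laboratory contact with scheduled cultures could raise the later one. The culture clause may also attach only to the microscopy branch. Complaint plus positive dipstick would then qualify, p could be close to 1, and the shift would nearly vanish. All of this stands.

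Fourth, p is assumed. A reader might go on to p = 0.5, where the fixed-SD formula gives 79% at b = 3; nothing in the documents supports a share that low.

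**Conclusion.** The concern holds for the within-arm UTI test and for the 80% and 97% figures attached to it. As planned, that test can be significant without a treatment effect, because it compares two counts that are not shown to share a definition. The likely direction is a false drop.

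For 2 to 4 historical UTIs per 6 months and a 70–90% share meeting the study definition, the chance in one arm is about 6–61% with the plan's SD of 1.7. With Poisson counts it is about 16–30% at 70%. The nominal rate is 2.5%. The lower figures deserve more weight, since the fixed SD inflates the upper ones. The rate and the share are assumptions, and the result also depends on how the culture clause is read.

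The between-arm comparison of changes is not biased by this mechanism, though it carries whatever noise the history brings. Within-arm tests on urodynamic and laboratory outcomes, which are assessed by the same procedures before and after, are not affected.

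**What to change.** Make the efficacy test for UTIs the between-arm comparison of on-study episodes that meet the study definition, over the same on-study window in every arm. A Poisson or negative binomial model with a log-time offset would serve. Enter the historical count as a covariate, with one stated source and look-back period for every participant. State whether the culture criterion applies to the dipstick branch as well as to microscopy.

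Report within-arm UTI change as descriptive only, and do not present the 80% and 97% figures as power for efficacy. The power for the between-arm test should be restated for the new analysis. The current 96% assumes a change of 0 with SD 0 without instillation; with SD 1.7 in both arms, the same difference of 2 has 79% power.

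Scoring past records against the study definition can be a sensitivity analysis. It should not be the rule for the baseline count: true episodes with incomplete records would drop out, which lowers the count and could reverse the bias.

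The cost is SAP wording, one added covariate, and the loss of the within-arm UTI test as an efficacy result. No treatment, visit or assessment changes.

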The potential research participant will be consented for participation and assessed for medical eligibility by the research team's Physiatrist, and/or Nurse Practitioner (as applicable). The Nurse Practitioner will conduct a medical history and physical examination and determine medical eligibility based on the clinical inclusion criteria and exclusion criteria and consideration of the risk assessment specific for the individual based on their medical history and examination. Following medical clearance for the assessments, the potential research participant will undergo urological assessments. Potential study eligibility will be determined by the investigators based on the evaluation of these assessments to be consistent with the inclusion criteria. The participant will then complete the bladder washout protocol for the study for 80 days and may continue with his/her current daily activities. Throughout the protocol, a number of assessments will be performed to assess the participant's progress in the study. Following the protocol, the participant will participate in post-instillation bladder assessments.

B. Consent and Eligibility Documentation

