Day-to-day oversight of the trial is provided by the Principal Investigators (PIs), Drs. [name] and [name]. They will review all study data and any adverse events, and report all adverse events to the Medical Monitor, sponsor, and University of Louisville IRB. Monitoring for the study will be provided by a Medical Monitor who will review study conduct including accrual, drop-outs, protocol deviations, and AEs in aggregate on an annual basis. The Medical Monitor will review serious adverse events (SAEs) in real-time. All data analyses (Labs, urodynamics, ultrasound) will be conducted as assessed with annual summary reports generated. Study data will be provided to the Medical Monitor to each annual review

one month prior. Data reports will be prepared by the principal investigators and the study statistician. The Medical Monitor will provide a written report to the study team with recommendations for study modification, study continuation/discontinuation as relevant. The study team is responsible for forwarding the report to the IRB.

Figure 2. Study Timeline.

Screening Phase		Intervention		Midpoint		Intervention			Post Intervention		
Assessments		Groups		Assessments		Groups			Assessments		
Labs	*Fxnl	Gent (n=12)	Saline (n=12)	None (n=12)	Labs	*Fxnl	Gent (n=12)	Saline (n=12)	None (n=12)	Labs	*Fxnl
UA Culture + Sensitivity	UDS US ~Intake forms	IC (n=6) 28.8 mg in 60 ml NS	IC (n=6) 60 ml NS	IC (n=6) No procedure	UA Culture + Sensitivity CBC CMP HCG	UDS US ~Intake forms	IC (n=6) 28.8 mg in 60 ml NS	IC (n=6) 60 ml NS	IC (n=6) No procedure SP (n=6) Catheter clamping for duration of instillation.	UA Culture + Sensitivity	UDS US ~Intake forms
CBC CMP HCG		SP (n=6) 28.8 mg in 60 ml NS	SP (n=6) 60 ml NS	SP (n=6) Catheter clamping for duration of instillation			SP (n=6) 28.8 mg in 60 ml NS	SP (n=6) 60 ml NS		CBC CMP HCG	
5 days		80 instillations - 7x/wk - 2x/d		5 days		80 instillations 7x/week – 2/d			5 days		

CBC, Complete Blood Count; CMP, Comprehensive Metabolic Panel; Gent, Gentamicin sulfate; IC, Intermittent Catheterization; Fxnl, Functional; HCG, Human Chorionic Gonadotropin (Pregnancy Test); NS, Normal Saline; SP, Suprapubic Catheter; UDS, Urodynamic Study; US, Ultrasound.

*The term "functional", abbreviated fxnl in this study, signifies an objective assessment of bladder functioning using urodynamic testing and ultrasound imaging.

IV. References

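### For continuous outcomes measured at visits, unadjusted change scores use the baseline inefficiently and drop participants who have a midpoint but no post value

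*Combined protocol and SAP*

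**What the plan says.** Section II.B.2 (Statistical Plan) is explicit about its inferential analyses, of which it names two: "pre-post differences within each group and between group comparisons of the differences". Within groups, "To evaluate the pre-post changes in each group, we will use paired t-test". Between groups, "To compare the changes between the 3 groups, we will use ANOVA test", followed by two-sample t-tests if the ANOVA is significant. Non-parametric equivalents replace these tests if assumptions fail. No baseline covariate, repeated-measures model or statistical missing-data method is named.

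Figure 2 shows two intervention blocks, the first given as "80 instillations - 7x/wk - 2x/d", with a midpoint assessment between them. The midpoint labs are "UA Culture + Sensitivity CBC CMP HCG", the same list as at screening and post-intervention. The functional tests are also repeated; a footnote says the term "signifies an objective assessment of bladder functioning using urodynamic testing and ultrasound imaging". Figure 2 plans 6 intermittent-catheter and 6 suprapubic participants in each arm.

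For people who leave early, the withdrawal paragraph of II.B.1 leaves the use of their data to the principal investigator's evaluation and allows an additional participant to be recruited.

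**The concern.** Hypothesis 1.2 concerns detrusor spasms, bladder compliance and the systolic pressure rise during cystometry. These are measured at visits in 12 people per arm, and II.B.2 gives no power for them, so precision matters.

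A change score subtracts the whole baseline value whatever its correlation with the later one. That adds noise which adjustment for baseline would avoid. A change score also needs a post value, so someone seen at baseline and midpoint only cannot enter the paired t-test or the ANOVA.

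Leaving may well be related to outcome: the discontinuation criteria in II.B.1 include a UTI that needs intravenous antibiotics. A comparison of completers could then be biased as well as smaller. Leaving such data to case-by-case judgement also allows the midpoint to be used ad hoc as a last value.

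**Working it through.** **The plan's own figures.** Inputs from II.B.2: 12 per arm, SD of change 1.7, two-sided 0.05. With the noncentral t on 11 degrees of freedom and noncentrality (change/1.7)·√12, paired power is 79.4% for a change of 1.5 (stated 80%) and 95.9% for a change of 2 (stated 97%). The unequal-variance test with SDs 1.7 and 0 gives 95.9% (stated 96%). These agree closely enough. They concern symptomatic UTI counts, and nothing below changes them.

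**Gain from baseline adjustment.** The documents give no between-visit correlation r. Assume equal variances (set to 1), a common r, and r from 0.3 to 0.7.

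- Change score: 2(1 − r)
- Post value adjusted for baseline: 1 − r²
- Ratio: (1 + r)/2

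| r | Change | Adjusted post | Ratio |
|---|---|---|---|
| 0.3 | 1.40 | 0.91 | 65% |
| 0.5 | 1.00 | 0.75 | 75% |
| 0.7 | 0.60 | 0.51 | 85% |

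No midpoint value enters this table.

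**What the midpoint adds to the post-visit contrast.** Suppose m of 12 per arm have baseline and midpoint but no post value. Let V be the variance of the quantity analysed and R the variance of the post value given baseline and midpoint, with covariances treated as known. The mean then has variance (V − R)/12 + R/(12 − m), and the effective n is V divided by this. With m = 0 it is 12, so the midpoint adds nothing.

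With a common correlation, R = 1 − 2r²/(1 + r). At r = 0.5 and m = 2, R = 0.667:

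- Change from baseline to post, V = 1.00: 0.333/12 + 0.667/10 = 0.0944, so the effective n is 10.59 against 10 complete pairs. The midpoint recovers 0.59/2 = 29% of the loss.
- Baseline-adjusted post, V = 0.75: 0.083/12 + 0.667/10 = 0.0736, so the effective n is 10.19. The midpoint recovers 9%, because baseline already explains part of what the midpoint would predict.

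For m from 1 to 4 and r from 0.3 to 0.7, under a common or a first-order autoregressive correlation, recovery is 22% to 48% on the change contrast and 4% to 31% on the baseline-adjusted contrast. No dropout rate is given, so m is an assumption.

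**Bias.** Simulated illustration, all inputs assumed: the true difference is 1.0 SD at post and 0.5 SD at midpoint, and participants leave when their midpoint change is worse than a cut-off that removes 10% to 30% of controls. The completers' change-score difference is then 0.88 to 0.95 SD. Adjusting completers for baseline gives 0.92 to 0.98. Using the midpoint as well restores 1.00, because leaving then depends only on observed values.

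**Averaging midpoint and post.** Like for like, the average change has variance 1.5(1 − r) against 2(1 − r), which is 25% lower at every r. This is a different estimand. The first block lasts 80/2 = 40 days. The gentamicin instillation section spreads dwell-time escalation over 3 to 4 weeks, or 21 to 28 of those days (the 1 to 2 laboratory weeks in II.B would be 7 to 14). If the midpoint effect were half the post effect (assumption), the average would be 0.75 of it. At r = 0.5 the adjusted average has variance (1 + r)/2 − r² = 0.50, so its signal-to-noise relative to adjusted post is 0.75/√(0.50/0.75) = 0.92, a loss.

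**The case against.** Change-score t-tests and ANOVA are valid under randomisation and simple to report, a reasonable choice for a 36-person feasibility study. That stands: the issue is efficiency and handling of early leavers, not validity with complete data.

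A reader might infer that the midpoint tests are wasted. The documents do not support this. Section III.A says "Throughout the protocol, a number of assessments will be performed" and gives following the participant's progress as the purpose. Section III.E.5 has labs, urodynamics and ultrasound analysed as they are done and summarised each year. II.B.2 summarises data without restricting visits, and midpoint chemistry bears on the renal discontinuation criteria. Only the inferential role is missing.

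A reader might also credit the midpoint with a large gain, since the adjusted average of midpoint and post has 40% to 60% of the change-score variance (0.56/1.40 to 0.36/0.60). Part of that is baseline adjustment and the rest comes from changing the estimand. Nor are change scores always the least precise choice: at r = 0.7 their variance is 0.60, against 1.00 for unadjusted post values.

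Finally, the loss of early leavers follows from the form of the tests and is not stated. The investigator's discretion and the option to recruit another participant soften it, but neither is a prespecified analysis rule.

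**Conclusion.** The point holds as a low-severity improvement for continuous outcomes measured at visits: urodynamics, blood pressure during cystometry, and labs. The main gain is baseline adjustment, with 65% to 85% of the change-score variance (75% at r = 0.5), given equal variances and r between 0.3 and 0.7.

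The midpoint's contribution is secondary. It adds no precision to the post-visit contrast if data are complete. With dropout it recovers a minority of the lost information, and less once baseline is adjusted for. Its stronger justification is protection against bias when leaving depends on midpoint results. Early leavers would contribute, but not as if they had been fully observed.

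UTI and antibiotic counts, and categorical outcomes such as dyssynergia type and hydronephrosis grade, need other methods.

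**What to change.** In II.B.2, for continuous outcomes measured at visits, replace the between-group ANOVA on changes with a repeated-measures model:

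- midpoint and post values as outcomes;
- baseline value and catheter type as covariates;
- arm, visit and arm-by-visit;
- a simple covariance structure and small-sample degrees of freedom.

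Make the post-visit contrast the main result and report the average over both visits as supportive only. State that everyone with at least one post-baseline value enters, and on what assumption about missing data, in place of case-by-case judgement. Fix this before unblinding.

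The cost is SAP wording and slightly more analysis, with no new visits or procedures. The two covariates take two degrees of freedom: for a single-visit comparison of 36 participants, the residual falls from 36 − 3 = 33 to 36 − 5 = 31. At 12 per arm further covariates should be avoided.
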